8.3.3. Study Outcomes

AESIs, as defined in Section 8.3.4.1, will be identified, with a date of diagnosis, using predefined validated algorithms (as possible), based on diagnosis codes (with procedure and/or pharmacy dispensing codes and/or limited to specific medical care settings if applicable to the outcome).

8.3.4. Evaluation of Safety Outcomes

Within Janssen, a list of AESIs has been created based on current knowledge of the Ad26.COV2.S vaccine and potential risks related to adenovirus vaccine platform. Table 1 lists the AESIs to be ascertained in the study with specific risk windows and background incidence rates.

8.3.4.1. Case Ascertainment and Validation Process

The incidence of AESIs following administration of the Ad26.COV2.S vaccine or the BNT162b2 vaccine will be ascertained in claims data using claims algorithms. Case validation to confirm the algorithm and/or disease diagnosis and date of onset may be conducted for high priority AESIs that are judged likely to be subject to misclassification based on clinical expert opinion, prior validation studies (if available), and researchers familiar with the data sources, including the Data Partners. Review of medical records or chronological listings of diagnosis, procedure, and pharmacy dispensing codes in health insurance claims profiles by clinicians may be conducted. depending on the AESI. Where available, Brighton Collaboration definitions or any other clinical definitions from published literature or learned societies will be used as case definitions if medical record review is implemented for the AESI. For outcomes selected for validation, a sampling strategy may be implemented based on the number of algorithm-identified events to select cases that are eligible for case validation. Published validation estimates of the algorithms used may also be considered to inform or adjust relative risk estimates. If the positive predictive value (PPV) of a given AESI is above a prespecified threshold (eg, $\geq 80\%$), all identified cases in the electronic data will be included in the final analysis. If the PPV is lower than the prespecified threshold (eg. < 80%), then the validation results or published validation estimates will be used to inform or adjust relative risk estimates (eg, complete case analysis for the SCRI design or quantitative bias analysis for the active comparative design) in the electronic data. The PPV threshold for determining whether all cases identified in claims data are to be included in final analysis will be specific to each AESI and will depend on the background rate of each AESI. The sampling strategy, the selection of which high priority AESIs to be validated and the rationale for selection, details on the validation methods, and the plan for integrating the validation results into the final analysis will be described in the data validation plan.

8.3.4.2. Risk Windows

Status: Approved, Date: 20 October 2022

Table 1: AESI-Specific Risk Windows and Background Incidence Rates

Body system	AESI	Disease-specific washout period before administration of Ad26.COV2.S or BNT162b2 for active comparator design	Disease- specific washout period before event for SCRI design	Disease- specific risk period following the administration of Ad26.COV2.S or BNT162b2	Range of adult background rates per 100,000 person- years reported in the external literature ^{a,b}
Nervous and central nervous system	Encephalitis, including ADEM & meningoencephalitis	180 days	180 days	1-42 days	2-73 (Li X et al. 2021; Baker MA et al. 2013; Ostropolets A et al. 2022; Esposito D et al. 2018)
	Guillain-Barré Syndrome	365 days	365 days	1-42 days	< 1-23 (Baker MA et al. 2013; Li X et al. 2021; Klein NP et al. 2010; Ostropolets A et al. 2022; Esposito D et al. 2018)
	Transverse myelitis	365 days	365 days	1-42 days	< 1-5 (Baker MA et al. 2013; Li X et al. 2021; Klein NP et al. 2010; Ostropolets A et al. 2022)
	Bell's palsy	180 days	180 days	1-42 days	40-174 (Li X et al. 2021; Baker MA et al. 2013; Ostropolets A et al. 2022)
	Multiple sclerosis, including optic neuritis	All available	Not applicable for SCRI	1-365 days	2-29 (Alonso A and Hernán MA 2008; Klein NP et al. 2010; Esposito D et al. 2018)
	Sensorineural Hearing loss	365 days	365 days	1-21 days	12-81 (Alexander TH and Harris JP 2013)
	Generalized convulsions (without epilepsy)	180 days	180 days	1-14 days	25-120 (Kotsopoulos I et al. 2005)
	Generalized convulsions (with epilepsy)	365 days	365 days	1-14 days	14-62 (Kotsopoulos I et al. 2005)

CONFIDENTIAL – FOIA Exemptions Apply in U.S.

Body system	AESI	Disease-specific washout period before administration of Ad26.COV2.S or BNT162b2 for active comparator design	Disease- specific washout period before event for SCRI design	Disease- specific risk period following the administration of Ad26.COV2.S or BNT162b2	Range of adult background rates per 100,000 person- years reported in the external literature ^{a,b}
Immune system	Autoimmune thyroiditis	All available	Not applicable for SCRI	1-365 days	5-97 (Klein NP et al. 2010; Esposito D et al. 2018)
	Immune thrombocytopenia	365 days	365 days	1-42 days	1-56 (Baker MA et al. 2013; Klein NP et al. 2010; Li X et al. 2021; Ostropolets A et al. 2022; Esposito D et al. 2018)
	Thrombocytopenia	90 days	90 days	1-42 days	
	Type 1 diabetes mellitus	All available	Not applicable for SCRI	1-365 days	19-382 (Klein NP et al. 2010; Baker MA et al. 2013; Esposito D et al. 2018)
	Acute aseptic arthritis ^c	All available	Not applicable for SCRI	1-365 days	3-205 (Pennisi M et al. 2019; Esposito D et al. 2018)
	Anaphylaxis	180 days	180 days	0-2 days	7-85 (Lee S et al. 2017; Baker MA et al. 2013; Li X et al. 2021; Ostropolets A et al. 2022; Esposito D et al. 2018)
	Composite endpoint – Cardiac inflammatory disorders, including myocarditis and pericarditis	365 days	365 days	1-21 days	2-54 (Li X et al. 2021; Baker MA et al. 2013; Ostropolets A et al. 2022)
	Microangiopathy	365 days	365 days	1-28 days	
	Heart failure	All available	All available	1-28 days	812-5,020 (Cuthbertson CC et al. 2018) ^d
	Stress cardiomyopathy	365 days	365 days	1-28 days	
	Coronary artery disease, including acute myocardial infarction	All available	All available	1-28 days	41-823 (Manemann 2015)
	Acute myocardial infarction	180 days	180 days	1-28 days	6-1,514 (Li X et al. 2021; Ostropolets A et al. 2022)
	Arrhythmia	All available	All available	1-14 days	9-6,195 (Kjerpeseth LJ et al. 2021) ^e

CONFIDENTIAL – FOIA Exemptions Apply in U.S. Status: Approved, Date: 20 October 2022

Body system	AESI	Disease-specific washout period before administration of Ad26.COV2.S or BNT162b2 for active comparator design	Disease- specific washout period before event for SCRI design	Disease- specific risk period following the administration of Ad26.COV2.S or BNT162b2	Range of adult background rates per 100,000 person- years reported in the external literature ^{a,b}
Blood and lymphatic system	Deep vein thrombosis	180 days	180 days	1-28 days	66-1,206 (Li X et al. 2021; Huang W et al. 2014; Ostropolets A et al. 2022)
disorders	Pulmonary embolism	180 days	180 days	1-28 days	20-427 (Li X et al. 2021; Huang W et al. 2014; Ostropolets A et al. 2022)
	Disseminated intravascular coagulation	180 days	180 days	1-28 days	< 1-203 (Li X et al. 2021; Singh B et al. 2013; Ostropolets A et al. 2022)
	Non-hemorrhagic stroke	180 days	180 days	1-28 days	17-1,523 (Li X et al. 2021; Feigin VL et al. 2015; Ostropolets A et al. 2022)
	Hemorrhagic Stroke	180 days	180 days	1-28 days	13-506 (Li X et al. 2021; Feigin VL et al. 2015; Ostropolets A et al. 2022)
	Cerebral venous thrombosis	180 days	180 days	1-28 days	< 1-1.7 (Coutinho JM et al. 2012)
	Peripheral arterial thrombosis	180 days	180 days	1-28 days	, , , , , , , , , , , , , , , , , , ,
	Thrombosis with thrombocytopenia syndrome	180 days	180 days	1-28 days	2-362 (Biologics Effectiveness and Safety (BEST) Initiative 2021)
	Composite endpoint – Venous thrombosis (including PE and DVT)	180 days	180 days	1-28 days	
	Composite endpoint – Arterial thrombosis (including coronary artery disease and non-hemorrhagic stroke)	180 days	180 days	1-28 days	108 (Huang W et al. 2014)

Body system	AESI	Disease-specific washout period before administration of Ad26.COV2.S or BNT162b2 for active comparator design	Disease- specific washout period before event for SCRI design	Disease- specific risk period following the administration of Ad26.COV2.S or BNT162b2	Range of adult background rates per 100,000 person- years reported in the external literature ^{a,b}
	Composite endpoint – Stroke (includig non-hemorrhagic and hemorrhagic strokes)	180 days	180 days	1-28 days	
Renal system	Acute kidney failure	365 days	365 days	1-14 days	20.9 (Liaño F, Pascual J, and Madrid Acute Renal Failure Study Group 1996)
Hepatic system	Acute hepatic failure	All available	All available	1-14 days	0.55 (Bower WA et al. 2007)

ADEM = acute disseminated encephalomyelitis; AESI = adverse event of special interest; CI = confidence interval; DVT = deep vein thrombosis; PE = pulmonary embolism.

^a 95% CIs not provided for background rate ranges.

b Details of rate calculations: Age-stratified rates: Baker, Esposito, Kostopolous, Coutinho; Age- and sex-stratified rates: Li, Ostroplets, Klein, Alexander, Lee, Manemann, Kjerpeseth, Singh; Crude rates: Liaño, Bower; Other: BEST (age- and data source-stratified), Cuthbertson (age-, sex-, and race-standardized, stratified by inpatient/outpatient setting), Huang (age- and sex- standardized), Alonso & Hernán (age-standardized, stratified by sex), Feigen (age-standardized), Pennisi (unknown)

^c Note that the phenotype implemented was labeled "arthritis" broad, non-specific to aseptic arthritis.

^d Heart failure rate estimated among individuals aged 65 years and older.

^e Outcomes restricted to inpatient or fatal atrial fibrillation, 2014.

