- composite endpoints within 1-28 days in individuals vaccinated with the Ad26.COV2.S vaccine and in corresponding individuals vaccinated with the BNT162b2 vaccine or during a control window within the same individual
 - o venous thrombosis, including PE and DVT
 - o arterial thrombosis, including coronary artery disease and non-hemorrhagic stroke
 - o stroke, including non-hemorrhagic and hemorrhagic strokes
- the incidence of encephalitis (including acute demyelinating encephalomyelopathy and meningoencephalitis), Guillain Barré Syndrome, Bell's palsy, immune thrombocytopenia, thrombocytopenia, and transverse myelitis within 1-42 days in individuals vaccinated with the Ad26.COV2.S vaccine and in corresponding individuals vaccinated with the BNT162b2 vaccine, or during a control window within the same individual.
- the incidence of autoimmune thyroiditis, acute aseptic arthritis, multiple sclerosis (including optic neuritis), and Type 1 diabetes mellitus **within 1-365 days** in individuals vaccinated with the Ad26.COV2.S vaccine and in corresponding individuals vaccinated with the BNT162b2 vaccine.

Secondary Objective

• The secondary objective for this study is to describe the number of individuals who received a second dose of Ad26.COV2.S as well as their baseline demographic characteristics.

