8.2.2.2.3. Exclusion Criteria for Exposed and Active Comparator Cohorts

Individuals will be excluded from the exposed and active comparator cohorts if:

- 1. They have been vaccinated with any COVID-19 vaccines at any time prior to the reference date.
- 2. They had records of more than 1 COVID-19 vaccine brand on the reference date.
- 3. They are aged < 18 years on the reference date.

Individuals with diagnosis of any of the AESIs in the AESI-specific washout periods prior to the reference date (Section 8.3.4.2) will not be excluded from the overall study population. However, individuals with diagnoses of AESIs in outcome-specific washout periods before the reference date will be excluded from outcome-specific analyses of those AESIs. Washout periods for each AESI are defined in Table 1.

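### The arterial-thrombosis composite has a 180-day washout while its coronary artery disease component has an all-available one, so CAD last coded more than 180 days ago can count as incident in the composite only

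*Protocol*

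**What the plan says.** Table 1 in Section 8.3.4.2 sets a washout for each outcome, one column for the active-comparator cohort and one for the self-controlled risk interval (SCRI) design. The relevant rows, each with cohort washout, SCRI washout and risk period, are:

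- CAD: "Coronary artery disease, including acute myocardial infarction All available All available 1-28 days"
- AMI alone: "Acute myocardial infarction 180 days 180 days 1-28 days"
- Non-hemorrhagic stroke: "Non-hemorrhagic stroke 180 days 180 days 1-28 days"
- Composite: "Arterial thrombosis (including coronary artery disease and non-hemorrhagic stroke"), with 180 days, 180 days and 1-28 days

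Section 7 lists the composite among the primary endpoints as "arterial thrombosis, including coronary artery disease and non-hemorrhagic stroke", so its coronary component is CAD as a whole and not AMI only.

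The washouts are fixed in the protocol and are not deferred. Section 8.2.2.2.3 says "Washout periods for each AESI are defined in Table 1" and excludes people outcome by outcome. Section 8.2.2.1 applies the same table to the SCRI design, which is primary for this 1-28 day outcome. The definitions list describes the washout as a means of identifying incident cases more plausibly. Section 8.2.2.2 says all baseline data are used for some chronic conditions.

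**The concern.** The same claim gets opposite status in two primary analyses. Take a person whose last CAD code lies more than 180 days back and who has no stroke code within 180 days. The CAD analysis removes this person as non-incident. The composite analysis keeps the person, and a new CAD code in the window counts as an arterial-thrombosis event.

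If that new code records established disease and is unrelated to vaccination, such events add to both the risk and control windows (or to both cohorts) and dilute any real excess. For a safety study that is the unfavorable direction, and Section 6.1 names thromboembolic events among the emerging concerns under evaluation.

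**Working it through.** **Table comparison.** Washouts of the thrombosis and stroke composites against their separately listed components; each entry is the same in both designs.

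| Composite | Composite washout | Component washouts |
|---|---|---|
| Venous thrombosis | 180 days | DVT 180 days; PE 180 days |
| Stroke | 180 days | non-hemorrhagic 180 days; hemorrhagic 180 days |
| Arterial thrombosis | 180 days | CAD all available; non-hemorrhagic stroke 180 days |

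Only the arterial composite has a washout shorter than that of a listed component. No rule in the protocol carries component washouts into a composite, and none explains the shorter period.

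**Illustration 1: dilution of the IRR.** The protocol states no figure to reproduce here. Every input is an assumption: 5-8% of vaccinees have established CAD, 10-15% of those go uncoded for 180 days, 5-10% of those are re-coded in a 28-day window, and the true event rate is 300-1,000 per 100,000 person-years.

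- Re-coded events per 100,000 per window, F = 100,000 × prevalence × share uncoded × re-code probability. Low: 100,000 × 0.05 × 0.10 × 0.05 = 25. High: 100,000 × 0.08 × 0.15 × 0.10 = 120.
- True events, T = rate × 28/365.25. Low: 300 × 28/365.25 = 23. High: 1,000 × 28/365.25 = 77.
- Observed IRR for a true IRR of 2 = (2T + F)/(T + F). Worst pairing: (46 + 120)/(23 + 120) = 1.16. Best pairing: (154 + 25)/(77 + 25) = 1.75.

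If a care-setting restriction cut the re-code probability to one-tenth (also an assumption), F becomes 2.5 to 12. The observed IRR is then (46 + 12)/(23 + 12) = 1.66 to (154 + 2.5)/(77 + 2.5) = 1.97.

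**Illustration 2: SCRI power.** The signed-root likelihood-ratio formula, with equal windows (r = 0.5) and two-sided alpha 0.05, is:

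- m = RR·r + 1 − r
- A = 2[(RR·r/m)·ln RR − ln m]
- B = (ln RR)²/A × RR·r(1 − r)/m²
- power = Φ[(√(nA) − 1.96)/√B]

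It reproduces all seven Table 2 entries checked. For 100 events and a relative risk of 2: m = 1.5, A = 0.1133, B = 0.943, power = Φ[(3.366 − 1.96)/0.971] = 0.926, as printed.

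Let f be the share of control-window composite events that are re-coded CAD with an IRR of 1. The observed IRR is (1 − f) × 2 + f. Holding total events at 100:

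| f (assumed) | Observed IRR | Power |
|---|---|---|
| 0 | 2.00 | 0.926 |
| 0.10 | 1.90 | 0.885 |
| 0.25 | 1.75 | 0.788 |
| 0.50 | 1.50 | 0.519 |
| 0.75 | 1.25 | 0.198 |

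The documents give no value for f.

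**The case against.** **No inheritance rule.** The protocol nowhere says that a composite must take its components' longest washout, and Table 1 does not follow one consistently: AMI has 180 days alone but all available history inside the CAD row. A 180-day washout lets recurrent infarction and stroke count, which is defensible for an acute composite. This stands as a reason to keep 180 days for AMI and stroke. It does not explain why non-AMI CAD is non-incident in one row and incident in the other.

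**The algorithm is not shown.** Section 8.3.3 allows algorithms limited to particular care settings. An acute or inpatient CAD algorithm would remove many routine re-codings. This stands, and it governs the size. Also, CAD that is coded regularly would often have a code within 180 days and be excluded anyway.

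**Partial safeguards.** CAD, AMI and non-hemorrhagic stroke are each analyzed separately, so a diluted composite need not hide a component signal. Section 8.7.3 stratifies on a history of the event more than a year earlier, which would make some dilution visible. Section 8.3.4.1 permits validation. But the stratum is a subgroup analysis that leaves the main estimate unchanged, and it misses people whose only codes lie 181 to 365 days back. Validation is optional. The prior-event indicators in Section 8.3.2 enter the propensity score and exclude nobody.

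**Direction.** A reader might infer that re-codings must fall equally in both windows. That is not assured: a vaccination visit that prompts chronic-disease coding could push the IRR the other way.

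**Conclusion.** The mismatch is real on the face of Table 1 and applies in both designs. It is unexplained, and nothing in the protocol removes the affected people from the main composite estimate. A pull toward an IRR of 1 is the expected direction, on the condition that the CAD algorithm captures re-coded established disease and that the re-coding is unrelated to vaccination.

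Two stronger readings are tempting and not supported. One is that the composite IRR will be halved or worse: the 1.16 to 1.75 range rests wholly on assumed prevalence, coding gaps, re-code probability and true rate. The other is that CAD inherently needs an all-available washout: that standard is the protocol's own choice in its CAD row, and the point is one of internal consistency. This should be fixed before the final analysis; confidence is moderate.

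**What to change.** In both washout columns of the arterial-thrombosis row, replace the single 180 days with component-specific washouts:

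- a non-AMI CAD code counts only if there is no CAD code in all available history;
- AMI and non-hemorrhagic stroke keep the 180 days of their own rows.

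State explicitly that an AMI in a person with older CAD counts in the composite although the CAD row excludes it. Otherwise a residual difference between the two analyses would look like another error.

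Do not redefine the primary composite as AMI plus non-hemorrhagic stroke, since that would change a stated primary endpoint. At most, add it as a sensitivity analysis.

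The cost is two table cells and a line in the cohort definition. There will be somewhat fewer composite events, and those lost are ones the CAD row already treats as non-incident. The gain is limited by look-back: only 1 year of enrollment is guaranteed, and Section 8.4 puts about 25% of patients above 3 years, so for some members all available history is little more than 1 year.

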8.3.5. Follow-Up

8.3.5.1. SCRI Design

Individuals will be followed from the start of the risk window to the end of the control window (Figure 1). Control period definitions will be specific to each AESI and may be the same length or longer than the risk period. Control period definitions, including their placement relative to vaccination and length, will be defined in the SAP, taking into account the rareness and potential seasonality of each AESI. A buffer period may be included between the risk and control periods when the risk period is uncertain as documented in the literature. Postvaccination control windows will be used for the final analyses to avoid healthy vaccinee bias.

8.3.5.2. Cohort Design with Concurrent Active Comparator

Follow-up time for the primary objective evaluating the first dose of Ad26.COV2.S or the primary series of BNT162b2 will start on or the day after the reference date (depending on the specific AESI risk window) and will continue until the earliest of the following:

- date of first diagnosis of the AESI
- end of the duration of the disease-specific risk period (specified in Table 1; up to 1 year after the reference date)
- disenrollment from the health plan
- administrative end of study (eg, end of available data)
- death
- date of any COVID-19 vaccine that is a different brand than the index vaccine
- date of receipt of an additional or booster dose beyond the authorized primary series (ie, a second dose of COVID-19 vaccine in the Ad26.COV2.S cohort or a third dose of COVID-19 vaccine in the BNT162b2 cohort)

The authorized primary series of BNT162b2 consist of 2 doses, spaced 21 days apart. If the AESI-specific risk period after dose 1 of BNT162b2 ends before a second dose is received, follow-up will end at the end of the dose 1 disease-specific risk period. However, a second dose of BNT162b2 may be received during the dose 1 disease-specific risk periods of some AESI. If a second dose is received before the end of the AESI-specific risk period, the risk periods of dose 1 and dose 2 will be concatenated into a single risk period, and follow-up will end after the duration of the disease-specific risk period following dose 2. To address differential lengths of follow-up time between the exposed and comparator cohorts that will arise from including second doses of BNT162b2 in the comparator cohort, modifications of this criteria will be evaluated in sensitivity analyses (Section 8.7.5).

Note that follow-up time will not be censored if a diagnosis of COVID-19 occurs after the initial vaccine dose. Only severe COVID-19 that arises to medical attention will be captured given the nature of the available data. This information will be captured and used in descriptive analyses.

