8.1.1.1. Self-controlled Risk Interval Design (Primary Study Design for Acute Events)

The SCRI design will compare the risk of the AESIs in a postvaccination risk window to a postvaccination control window within the same individual, in a cohort of individuals vaccinated with Ad26.COV2.S (Figure 1). The use of a postvaccination control window (rather than a prevaccination control window) avoids bias due to healthy user vaccinee effect. To account for the possibility that increased risks of AESIs might extend beyond the risk interval, the risk and control windows may be separated by buffer periods for events that do not have well established risk intervals in the literature (to be defined in the statistical analysis plan [SAP]).

[figure not shown]

Figure 1: Self-Controlled Risk Interval Design

8.1.1.2. Cohort Design With Concurrent Active Comparator (Primary Study Design for Non-acute Events and Sensitivity Analysis for Acute Events)

[figure not shown]
For the cohort design, the incidence of AESIs will be compared between the 1-dose Ad26.COV2.S exposed cohort and the 2-dose BNT162b2 comparator cohort (Figure 2):

- **Exposed cohort**: individuals will have received at least 1 dose of Ad26.COV2.S administered according to US recommendations (BLA approval or EUA). The reference date will be the first date of receipt of Ad26.COV2.S.
- Active comparator cohort: individuals will have been vaccinated with at least 1 dose of the primary series of BNT162b2 at any time on or after the start of the study observation period. The reference date of the comparator cohort will be the calendar date of the first dose in the primary series of BNT162b2. Individuals will be matched by propensity scores (PS) and calendar time (within 2 weeks) at the reference date using a 1:4 ratio of exposed to comparator within the Data Partner distributed database, if feasible; the matching ratio will be dependent on the findings of the relative uptake of vaccinations identified during feasibility assessments and monitoring.

COVID-19 vaccines were first administered to priority populations at high risk of severe disease or exposure, including older adults or those with comorbidities. Therefore, information on the presence of comorbidities within 1 year prior to the reference date and older age will be collected and included in the PS models. The covariates for the propensity score models, to be assessed up to the reference date, are described in Section 8.7.2.1.

[figure not shown]

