Cohorts will be defined utilizing existing secondary healthcare data sources. One year of medical and pharmacy insurance enrollment prior to the reference date will be required to determine whether individuals meet the study criteria and to define baseline characteristics. Data on the occurrence of AESI will be extracted within the 1 year after the reference date.

Figure 2: Cohort Study Design

[figure not shown]
Ad26.COV2.S exposed cohort

Outcome-specific follow-up periods after vaccine receipt

Comparator BNT162b2 exposed cohort

Outcome-specific risk periods after dose 1 for outcomes with risk windows \leq 21 days

Comparator BNT162b2 exposed cohort

If vaccine dose 2 is received during the outcome-specific risk period after dose 1, the risk periods of dose 1 and dose 2 are concatenated into a single risk period, and follow-up ends after the duration of the outcome-specific risk period following dose 2. If vaccine dose 2 is not received, the outcome-specific risk window extends the full length from dose 1.

Outcome-specific risk windows:

- 2 days: anaphylaxis.
- 14 days: generalized convulsion, arrhythmia, acute kidney failure, acute hepatic failure.
- 21 days: cardiac inflammatory disorders, including myocarditis and pericarditis, and sensorineural hearing loss.

- 28 days: microangiopathy, disseminated intravascular coagulation, DVT, pulmonary embolism, hemorrhagic and non-hemorrhagic stroke, acute myocardial infarction, coronary artery disease (including acute myocardial infarction), heart failure, stress cardiomyopathy, venous thrombosis composite endpoint, arterial thrombosis composite endpoint, stroke composite endpoint.
- 42 days: encephalitis (including acute demyelinating encephalomyopathy and meningoencephalitis), Guillain Barré Syndrome, Bell's palsy, immune thrombocytopenia, thrombocytopenia, transverse myelitis.
- 365 days: autoimmune thyroiditis, acute aseptic arthritis, multiple sclerosis (including optic neuritis), Type 1 diabetes mellitus.

Note that follow-up time for the primary analysis will end upon receipt of a booster dose of Ad26.COV2.S or a booster dose of any COVID-19 vaccine.

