8.7.5. Sensitivity Analyses

8.7.5.1. Extended Disease-specific Risk Periods

Sensitivity analyses will be performed to assess the risk of AESI within extended disease-specific risk periods for events for which the risk interval is not well known or not currently documented in the vaccine safety literature. These extended disease-specific risk periods will be further described in the SAP.

8.7.5.2. Alternate Follow-up Criteria for Active Comparative Design Based on BNT162b2 Dose (for Non-acute Events)

As described in Section 8.3.5.1, for the primary analysis of non-acute events evaluated using a cohort design, if the disease-specific risk period after dose 1 of the comparator vaccine (BNT162b2) overlaps with the receipt of dose 2, the risk periods for dose 1 and dose 2 will be concatenated together into a single risk period. Sensitivity analyses will be conducted for non-acute events using a cohort design with the active comparator after receiving only a single dose (Figure 4) or after receiving both doses (Figure 5) of the comparator vaccine. Note that sensitivity analysis with the active comparator after receiving only a single dose will be performed only for AESI with risk periods of 21 days or longer (where overlap of the dose 1 risk period with dose 2 of BNT162b2 is expected), as this sensitivity analysis will be identical to the primary analysis if the dose 1 and dose 2 risk periods do not overlap.

exposed cohort: receives only

1 dose

[figure not shown]
T = 0;Vaccine dose Vaccine dose 1 receipt 2 receipt 1-year minimum continuous health plan enrollment: Inclusion/exclusion criteria Risk window assessment window Baseline characteristics Comparator assessment window BNT162b2 exposed cohort: receives 2 doses If vaccine dose 2 is received during the outcome-specific risk period after dose 1, the risk period is censored on the date of dose 2. T = 0: Vaccine dose 1 receipt 1-year minimum continuous health plan enrollment: Inclusion/exclusion criteria Risk window assessment window Baseline characteristics Comparator assessment window BNT162b2

If vaccine dose 2 is not received, the outcome-specific

risk window extends the full length from dose 1.

Cohort Study Design for Sensitivity Analysis After Only a Single Dose of BNT162b2 Figure 4:

Figure 5: Cohort Study Design for Sensitivity Analysis After Both Doses of BNT162b2

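### For the four 365-day AESIs, Section 8.3.5.2 gives two incompatible end dates for comparator follow-up: at most 1 year after dose 1, or dose 2 plus 365 days

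*Protocol*

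**What the plan says.** The cohort design is the primary design only for the non-acute AESIs, all with a one-year window: "365 days: autoimmune thyroiditis, acute aseptic arthritis, multiple sclerosis (including optic neuritis), Type 1 diabetes mellitus" (Section 8.1.1.2, Figure 2 text). Time zero for the comparator is dose 1: "The reference date of the comparator cohort will be the calendar date of the first dose in the primary series of BNT162b2".

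Section 8.3.5.2 stops follow-up at the earliest of several events. One is the end of the disease-specific risk period, qualified as "specified in Table 1; up to 1 year after the reference date". The section then notes that "The authorized primary series of BNT162b2 consist of 2 doses, spaced 21 days apart", and says that when dose 2 arrives before the dose 1 window closes, the two windows are joined and "follow-up will end after the duration of the disease-specific risk period following dose 2".

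On event capture, Section 8.1.1.2 says: "Data on the occurrence of AESI will be extracted within the 1 year after the reference date". The Abstract says the same.

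Section 8.7.5.2 restates the joining rule for the primary analysis of non-acute events. Its stopping rule for the both-dose comparison refers to the risk period after dose 2 of BNT162b2, yet keeps the limit of 1 year after the reference date in the same bullet.

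For short windows, the Figure 2 label reads "Outcome-specific risk periods after dose 1 for outcomes with risk windows" of 21 days or less. Section 8.3.5.2 sets no such threshold. Section 8.7.5.2 puts windows of 21 days or longer in the group "where overlap of the dose 1 risk period with dose 2 of BNT162b2 is expected".

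**The concern.** At the stated spacing, dose 2 always falls inside a 365-day window, so the joining rule is triggered for every comparator who completes the series and is still under follow-up at dose 2. One sentence of Section 8.3.5.2 then stops that person at day 365 and another at about day 386. The text does not say which prevails.

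If the cap prevails, joining the windows does nothing for the 365-day AESIs. Yet Section 8.7.5.2 applies joining to exactly these outcomes, and Section 8.3.5.2 expects unequal follow-up between cohorts because of it. If joining prevails, comparator time runs beyond the period in which events are to be extracted.

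At stake are the numerator and denominator of the comparator rate in every primary cohort result. Section 8.7.1.2 defines that rate as cases divided by follow-up person-time. The programs are written centrally and run at four Data Partners, so an unresolved end date would be settled by a programming choice.

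**Working it through.** **Inputs.** Window 365 days (Table 1); reference date = dose 1 (8.1.1.2); dose spacing 21 days (8.3.5.2); event extraction to 1 year (8.1.1.2). For a plausible spread of dose 2, days 17 to 28 are borrowed from the stopping rules of the both-dose sensitivity analysis (8.7.5.2). The primary analysis sets no such limits.

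**The plan's own cohort figure.** Section 8.5.2 gives 0.805 for the probability that the upper 95% limit is below 3.0, with 100,000 exposed, 400,000 comparators, 60 days each, 50 per 100,000 person-years and a true relative risk of 1.0. Expected events are 100,000 × 60/365 × 0.0005 = 8.22 and four times that, 32.88. SE = √(1/8.22 + 1/32.88) = 0.390. Φ(ln 3/0.390 − 1.96) = 0.804, which reproduces the stated value. The calculation assumes equal 60-day windows, so it says nothing about the conflict.

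**End dates, 365-day AESIs.** Cap: day 365. Joined windows: d + 365, where d is the day of dose 2.

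| Dose 2 on day | Joined end | Extra days | (365 + d)/365 |
|---|---|---|---|
| 17 | 382 | 17 | 1.047 |
| 21 | 386 | 21 | 1.058 |
| 28 | 393 | 28 | 1.077 |

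**Case A: person-time to d + 365, events only to day 365.** With a constant hazard and everyone followed to the end, the comparator rate is multiplied by 365/(365 + d). For d = 21 this is 365/386 = 0.946, so the IRR is multiplied by 386/365 = 1.058. The range is 1.047 to 1.077 for days 17 to 28.

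Only people still followed at day 365 add the extra time. As an illustration with assumed values, if 30% remain and mean follow-up is 250 days, the factor is about 1 + 0.3 × 21/250 = 1.025.

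**Case B: events and person-time cut on the same day.** Let the hazard in days 366 to 386 be k times the earlier hazard (assumed). The IRR with joined windows, relative to the capped IRR, is 386/(365 + 21k):

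- k = 0.5: 386/375.5 = 1.028
- k = 1: 386/386 = 1.000
- k = 2: 386/407 = 0.948

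**21-day AESIs (sensitivity analysis only).** The Figure 2 label ends follow-up at day 21. Joining ends it at day 38 for dose 2 on day 17 and at day 41 for day 20, which is 38/21 = 1.81 to 41/21 = 1.95 times the time. For dose 2 exactly on day 21, Section 8.3.5.2 does not clearly say whether it falls inside the window.

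With dose 2 on day 17 and a post-dose-2 hazard k times the dose 1 hazard (assumed), the relative comparator rate is (17 + 4k)/21 under the label and (17 + 21k)/38 when joined. The joined IRR divided by the label IRR is:

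- k = 0.5: 0.905/0.724 = 1.25
- k = 1: 1.00
- k = 2: 1.190/1.553 = 0.77

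**The case against.** The best defence is that the cap already governs. Section 8.3.5.2 uses an earliest-of list, and Section 8.7.5.2 attaches the same 1-year limit to the period after dose 2, which suggests an overall ceiling. On that reading follow-up is at most 365 days in both cohorts and nothing is biased. The reading is available but not settled, because it leaves the joining rule with no effect on the outcomes to which Section 8.7.5.2 expressly applies it.

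A second objection is that no passage prescribes Case A. It combines the joining rule with a sentence on data extraction that may only describe scope. That stands: Case A is a risk created by the wording, not the stated analysis. Its factors are also ceilings, because follow-up also ends at a third dose, a different brand, disenrollment, death or the end of data.

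A reader might infer that the error always runs against Ad26.COV2.S, or that it could reach 1.16 or 1.33. The direction is fixed only in Case A. The larger factors, (365 + 60)/365 and (365 + 120)/365, need every comparator to receive dose 2 on day 60 or day 120, against a stated spacing of 21 days.

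The protocol does acknowledge unequal follow-up and plans single-dose and both-dose sensitivity analyses. These do not fix the primary end date: the first stops comparators at dose 2 and the second carries the same conflict.

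On the 21-day AESIs, the objection that this is minor is fair. Their primary design is self-controlled, and the Figure 2 drawing itself is not available here, only its label. A reader might also infer that Figure 2 stops comparators at dose 2. It does not: that is the rule of the single-dose sensitivity analysis.

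**Conclusion.** The contradiction is in the current text and affects the primary analysis of all four 365-day AESIs. The comparator end date is day 365 or, at the stated spacing, day 386 (days 382 to 393 for dose 2 on days 17 to 28).

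The effect on the IRR is conditional and modest. It is at most about 1.06 (1.05 to 1.08) if joined person-time is paired with one-year event extraction, assuming constant hazard and full follow-up. It is nil in expectation under a constant hazard if events and time are cut together. The documents do not support saying that the planned IRR is biased, only that the wording permits a biased implementation and leaves the end date open.

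The 21-day mismatch is real but confined to the cohort sensitivity analysis of acute events. There the choice matters only when dose 2 arrives within the window and the hazard differs after it.

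**What to change.** For the 365-day AESIs, state that follow-up and event capture in both cohorts end no later than day 365 after the reference date, so that joining the dose 1 and dose 2 windows does not extend them. Align Sections 8.1.1.2, 8.3.5.2 and 8.7.5.2, including the both-dose stopping rule. The cost is wording and one line in the censoring program. Relative to joined windows it gives up about 5% of comparator person-time at most at the stated spacing (21/386 = 5.4% with full follow-up, less with earlier censoring).

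For the 21-day AESIs, choose one threshold and use it in Figure 2 and in Sections 8.3.5.2 and 8.7.5.2, and say whether a dose 2 on the last day of the window counts as inside it. No new rule that stops follow-up at dose 2 is needed. That would change what the cohort analysis compares, and the single-dose sensitivity analysis already uses such a rule.
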